## 4.4 ENDPOINTS

### 4.4.1 Primary Endpoint

Changes in Visual Analog Scale (VAS) scores between baseline and follow up visits

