### 4.4.2 Secondary Endpoint

Difference in:

- Quality of Life (EQ-5D)
- Subject satisfaction
- Subject preference
- Incidence rate of adverse events

between standard burst stimulation and the two burst microdosing paradigms.

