### 12.0 STATISTICAL CONSIDERATIONS

#### 12.1 STATISTICAL DESIGN, HYPOTHESES, METHOD AND ANALYTICAL PROCEDURES

During baseline visit subjects will be randomized 1:1:1 to one of the three treatment sequences. An envelope-based system will be used for identifying which group the subject has been assigned. St. Jude Medical will provide sealed envelopes containing the site number and subject ID/sequence number. Inside the envelope, the randomization assignment will be identified along with the site number and subject ID/sequence number.

During reprogramming the subjects will not be made aware of what paradigm is currently being programmed. Pain questionnaires (VAS, EQ-5D, satisfaction and stimulation preference) will be administered by a clinician blinded to the currently programmed stimulation paradigm.

Scores from the subject's questionnaires as well as subject satisfaction will be compared between follow up visits using a repeated measure ANOVA under the hypothesis of equivalence between standard and burst microdosing stimulation paradigms.

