#### 12.2 SAMPLE SIZE

Considering the short time required for assessing the outcomes in each subject, we do not expect any drop-out. We will enroll up to 40 subjects, of these 30 are expected to be successfully screened and complete the study. Patients who fail screening will not participate in the study. This study is a feasibility trial, the sample power cannot be calculated because the effect size is not known. The sample size was selected to obtain early evidence and estimates of the effect size.

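### Section 12.1 plans a repeated-measures ANOVA across visits, but the objectives are two paradigm-minus-standard differences, which should be named and each given its own variance

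*Combined protocol and SAP*

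**What the plan says.** The only analysis sentence is in section 12.1. Questionnaire and satisfaction scores "will be compared between follow up visits using a repeated measure ANOVA", "under the hypothesis of equivalence between standard and burst microdosing stimulation paradigms". It does not name the contrasts, the error term, the covariance structure, any handling of unequal variances, a confidence interval, a significance level or an equivalence margin. No other section supplies them.

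The objectives are more specific. The primary objective (synopsis and section 4.3.1) compares standard burst with each of two microdosing paradigms, 5:5 and 5:10. The secondary endpoints (section 4.4.2) are differences "between standard burst stimulation and the two burst microdosing paradigms". The primary endpoint (section 4.4.1) is "Changes in Visual Analog Scale (VAS) scores between baseline and follow up visits".

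The design is a three-period crossover in which "subjects will be randomized 1:1:1 to one of the three treatment sequences". The sequences are cyclic, so each paradigm appears once in each period. On numbers, section 12.2 says "We will enroll up to 40 subjects, of these 30 are expected to be successfully screened and complete the study", adds that "we do not expect any drop-out", and states that "the sample power cannot be calculated because the effect size is not known". Sections 4.2 and 12.2 call this a feasibility study, and section 12.2 says that its size was chosen to give early evidence and effect-size estimates.

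**The concern.** The stated analysis does not by itself produce the two quantities that the objectives ask for, for three reasons.

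- **The factor.** Read literally, the comparison is between visits. Under the cyclic sequences every follow-up visit mixes all three paradigms across the groups, so a visit factor measures period, not paradigm. The sensible reading is that paradigm is the factor, but the text does not say so.
- **The test.** A conventional ANOVA with three levels gives one test on 2 degrees of freedom. That test also responds to 5:5 against 5:10, which is not an objective, and it does not say which paradigm, if either, differs from standard.
- **The error term.** Contrasts taken from such an ANOVA usually share one residual variance. This is correct only under sphericity, meaning that the three within-subject differences have equal variance. The two microdosing paradigms share burst settings and ON time and differ only in OFF time, so their scores may track each other more closely than either tracks standard. The pooled standard error would then be too small for both wanted contrasts. For an equivalence aim that is the unsafe direction, because narrow limits make microdosing look better established than it is. A sphericity correction to the omnibus F does not repair the contrasts.

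**Working it through.** **Inputs from the documents.** Thirty completers (section 12.2), three paradigms per subject, three cyclic sequences. No variance, correlation, significance level or margin is given, so there is no planned figure to reproduce. All correlations below are assumptions.

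**What is estimated.** If one baseline is subtracted from every follow-up VAS score, it cancels: (5:5 − baseline) − (standard − baseline) = 5:5 − standard. The argument is therefore the same for raw scores and for changes.

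**Formula.** Let v be the variance of each microdosing-minus-standard difference (taken as equal for the two) and w the variance of the 5:5-minus-5:10 difference. The pooled analysis estimates the variance of any difference as 2 × MSE, whose expectation is (2v + w)/3. Hence

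pooled SE / true SE = √[(2 + w/v)/3].

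With unit variances, v = 2(1 − r_s) and w = 2(1 − r_m). Here r_s is the correlation of each microdosing score with standard, and r_m is the correlation between the two microdosing scores.

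**Results.** The ratio is from the formula. The rejection rates are from simulation with 60,000 trials per case, n = 30, no true differences, and no period or carryover effects. The pooled test has 58 df.

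| r_s | r_m | v | w | w/v | SE ratio | Pooled test, nominal two-sided 5% |
|---|---|---|---|---|---|---|
| 0.6 | 0.75 | 0.8 | 0.5 | 0.625 | 0.935 | 6.6% |
| 0.6 | 0.8 | 0.8 | 0.4 | 0.5 | 0.913 | 7.2% |
| 0.5 | 0.8 | 1.0 | 0.4 | 0.4 | 0.894 | 8.1% |
| 0.5 | 0.9 | 1.0 | 0.2 | 0.2 | 0.856 | 9.5% |

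The paired contrast with its own variance (29 df) rejected 4.9%-5.1% of the time in all four cases. A separate simulation gave 95% interval coverage with the pooled error of 91.9% at w/v = 0.4 and 90.6% at w/v = 0.2.

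**Bound.** As w/v tends to 0 the ratio tends to √(2/3) = 0.816. In this symmetric pattern the standard error is therefore at most about 18% too small. If w = v, the ratio is 1 and there is no error.

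**A pattern that goes the other way.** Suppose similarity follows the share of time ON (100%, 50%, 33%), with assumed correlations of 0.75 for standard with 5:5, 0.55 for standard with 5:10, and 0.75 for 5:5 with 5:10. The three difference variances are 0.5, 0.9 and 0.5, with mean 1.9/3 = 0.633.

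- 5:5 minus standard: √(0.633/0.5) = 1.125. The pooled standard error is about 12% too large, and simulated rejection is about 2.9%.
- 5:10 minus standard: √(0.633/0.9) = 0.839. The pooled standard error is about 16% too small, and simulated rejection is about 10%.

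**Cost of separate variances when sphericity holds.** The 95% half-width in SDs of the difference is 2.045/√30 = 0.373 on 29 df, against 2.002/√30 = 0.365 on 58 df. The ratio 0.373/0.365 is 1.02, so intervals are about 2% wider.

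**The case against.** The strongest reply is that the plan never says that the error will be pooled or that only an omnibus test will be reported. Both are inferred from the name of the method, and a repeated-measures ANOVA can be run with multivariate or contrast-specific error. That is correct. A reader might infer that the trial's error bars are wrong, but the documents do not support this: they promise no interval and state no significance level, so no stated figure is in error. What stands is that the conventional form is the natural reading, that nothing in the text requires the better form, and that the choice is left open until the data are in.

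Second, the direction of the error is assumed. This also stands. The documents hold no variances or correlations, and the ON-time pattern above makes the pooled standard error for 5:5 too large. "More alike" must also mean a smaller variance of within-subject differences; similar means alone leave the standard errors unaffected.

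Third, this is a feasibility study. A reader might go further and ask for family-wise error control, a power comparison with the omnibus test, or a fixed testing order for the two paradigms. The documents do not support those steps: they set no significance level or margin, they rank neither paradigm, and a fixed order could block a conclusion on 5:10 after a chance miss on 5:5. The feasibility label does not answer the narrower point, however. Section 12.2 gives effect-size estimates as the reason for the sample size, and the effects in question are these two differences and their precision.

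**Conclusion.** The concern holds as a mismatch between the objectives and an under-specified analysis, with a better method available at little cost. The objectives need two paradigm-minus-standard differences. Section 12.1 names neither, and its conventional reading yields an omnibus test and a shared variance that is valid for each contrast only under sphericity.

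The size is conditional. With 30 completers and assumed correlations of 0.5-0.6 with standard and 0.75-0.9 between the microdosing paradigms, the pooled standard error is about 6%-14% too small for both contrasts, and a nominal 5% test rejects about 6.6%-9.5% of the time. The 18% limit applies when the two differences from standard have equal variance. Under other patterns the standard error for one contrast can be too large, so it should not be said that the plan generally understates uncertainty.

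The missing equivalence margin is a separate and larger gap, which this change does not close.

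**What to change.** In section 12.1, replace the visit comparison with the two differences 5:5 minus standard and 5:10 minus standard, named as the primary estimates. Estimate each with its own variance and report each with a confidence interval. The preferred model is a mixed model with paradigm and period as fixed effects, an unstructured within-subject covariance indexed by paradigm, and Kenward-Roger degrees of freedom. Simple paired differences also give each contrast its own variance but do not adjust for period, so they are second best.

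The cost is a paragraph of text, with no new data and no change to the design. If sphericity holds, intervals are about 2% wider (the paired calculation on 29 df). Estimating period effects may cost slightly more, as a few degrees of freedom are used.

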### Clinical Investigational Plan

	
After two weeks, subjects will return for the third follow up visit and complete questionnaires and assessments to evaluate the therapeutic efficacy of the third stimulation paradigm. Subjects will express their preference between the three burst stimulation paradigms, their IPGs will be programmed accordingly and they will exit the study.
 
Primary and secondary assessments will be compared between baseline and the two follow up visits.
 
The total duration of the study is expected to be 6 months.
 
The study will be conducted in a maximum of 4 centers in Europe

Devices used:	
Any commercially available SJM neurostimulation system:
 
 
• Implantable Pulse Generator (IPG)
 
• IPG Charger (in case of a rechargeable IPG)
 
• Clinician Programmer
 

Study Population	
The study population will consist of patients with chronic pain for failed back surgery syndrome or neuropathic back and/or leg pain with an implanted commercially available SJM spinal cord stimulation device and have been using conventional burst stimulation parameters for the past three months (Burst train consisting of 5 pulses, Intraburst frequency: 500 Hz, Burst rate: 40 Hz, Pulse width: 1000 μs). Up to 40 subjects will be enrolled in this study in up to 4 centers. Of these, it is expected that 30 subjects will be successfully screened and complete the study.
 
Patients will be considered for enrollment by the Principal Investigator as a candidate for the study at the study site if they meet the inclusion/exclusion criteria requirements, and agree to participate in the study.

Inclusion/Exclusion Criteria	
Inclusion Criteria
 
 
• Subject has been implanted with a commercially available SJM spinal cord stimulator for controlling chronic intractable pain associated with back and/or leg pain;
 
• Subject has been exclusively using burst stimulation for at least three months;
 
• Subject is 18 years of age or older;
 
• Subject’s pain-related medication regimen was stable in the 4 weeks prior to the screening evaluation;
 
• Subject agrees not to add or increase pain-related medication from enrollment through the study duration;
 
• Subject is willing to cooperate with the study requirements including compliance with the regimen and completion of all office visits;
 

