## Clinical Investigational Plan

### 3.0 RISKS AND BENEFITS OF THE CLINICAL STUDY

Subjects enrolled in this study will already have an implanted IPG programmed with burst stimulation as part of their standard pain management. In this study, we propose to evaluate alternative stimulation parameters that will deliver less current compared to the parameters already programmed in the stimulators. The subjects will not be required to discontinue or interrupt any current treatment prior to enrollment. During the study, the subjects will not be allowed access to the patient programmer and therefore will not be able to adjust therapy intensity. There is a possibility that the new stimulation parameters will not provide pain relief that is equivalent to the standard stimulation parameters, but optimal pain relief is expected to return on reuse of standard burst stimulation parameters. Although not expected, it is possible that the new stimulation parameters will instead improve pain relief. Use of these two new energy efficient stimulation parameters has the potential to prolong the battery life of a non-rechargeable, primary cell IPG by approximately 100% to 200%. It also has the potential to improve patient convenience by decreasing the frequency with which the patient has to recharge a non-primary cell IPG.

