### 3.8 RISK-TO-BENEFIT RATIONALE

The study will use devices currently approved as part of standard pain management care. As the alternate stimulations parameters will deliver less current compared to the standard treatment received by the subjects before enrolling in the study, the only risk entailed by this study is represented by the possibility that the pain relief afforded by the alternative microdosing paradigm might be inferior to the one provided by standard burst stimulation. Sequestering the patient programmer will prevent the subjects from adjusting therapy and can represent an inconvenience to the subjects, but is necessary to ensure blinding of the subjects.

Establishing equivalency between standard burst stimulation and more energy efficient stimulation paradigm could lead to a prolonging battery life up to 200% and/or shorter time for IPG recharging. This will reduce IPG replacement surgeries in primary cell stimulators and increased patient convenience in rechargeable stimulators.

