## Clinical Investigational Plan

paradigm. One week after this visit, the subject will be contacted to schedule the first follow up visit and instructed to start recording pain levels on the pain diary.

Two weeks after the screening visit, the subject will visit the clinic for the first follow up assessment. A Visual Analog Scale (VAS) score will be collected to determine pain levels during the first stimulation paradigm; the subject will also fill the EQ-5D and the satisfaction questionnaires administered by a clinician who is blinded to the stimulation paradigm. Subject's stimulators will be programmed with the second stimulation paradigm according to the group assignment. Stimulation intensity will gradually be increased until the subject perceives the stimulation to find the Threshold for Perception (TP), and then the intensity will subsequently be reduced to the sub-perception level providing optimal pain relief. Subjects will return the pain diary and will be provided with a new one for the assessment of the new stimulation paradigm. One week after this visit, the subject will be contacted to schedule the second follow up visit and instructed to start recording pain levels on the pain diary

Two weeks after the first follow up visit, the patient will return for the second follow up visit during which the efficacy of the second stimulation paradigm will be evaluated using the VAS, the EQ-5D and the subject satisfaction assessments administered by a clinician blinded to the stimulation paradigm. Subject's stimulators will be programmed with the third stimulation paradigm according to the group assignment. Stimulation intensity will gradually be increased until the subject perceives the stimulation to find the Threshold for Perception (TP), and then the intensity will subsequently be reduced to the sub-perception level providing optimal pain relief. Subjects will return the pain diary and will be provided with a new one for the assessment of the new stimulation paradigm. One week after this visit, the subject will be contacted to schedule the third follow up visit and instructed to start recording pain levels on the pain diary

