## 4.3 OBJECTIVES

### 4.3.1 Primary Objective

To compare differences in therapeutic efficacy between conventional burst stimulation parameters (Burst train consisting of 5 pulses, Intraburst frequency: 500 Hz, Burst Rate: 40 Hz, Pulse width: 1000  $\mu$ s) and energy efficient burst microdosing stimulation paradigms listed below:

- Standard burst stimulation parameters with 5 seconds of STIM ON, followed by 5 seconds of STIM OFF
- Standard burst stimulation parameters with 5 seconds of STIM ON, followed by 10 seconds of STIM

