Note: If a subject misses one or more of the scheduled follow up visits (inclusive of the assigned visit windows), this will be considered as a missed visit. If subject misses a visit, the subject will be asked to fill the one week pain diary again and the latest pain diary will be used for analysis. The subject may therefore still return for subsequent visits and will not be excluded from the study.

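### Section 12.1 attaches a hypothesis of equivalence to a repeated-measures ANOVA, which can only test for a difference, and it specifies no estimate or interval

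*Combined protocol and SAP*

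**What the plan says.** Section 12.1 is the only place that names a statistical method. Questionnaire and satisfaction scores are to be "compared between follow up visits using a repeated measure ANOVA under the hypothesis of equivalence between standard and burst microdosing stimulation paradigms". Neither that section nor any other gives an equivalence margin, a significance level, a confidence interval, or a rule for interpreting a non-significant F test.

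Other sections describe the aim in different terms:

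- Section 4.3.1 and the Synopsis word the primary objective as a comparison of differences: "To compare differences in therapeutic efficacy between conventional burst stimulation parameters" and the two microdosing paradigms.
- Section 3.8 states the benefit in terms of equivalence: "Establishing equivalency between standard burst stimulation and more energy efficient stimulation paradigm could lead to a prolonging battery life". Section 2.0 hypothesizes a similar clinical outcome without defining similar.
- Section 4.2 calls this a feasibility study. Section 12.2 says power cannot be calculated and adds: "The sample size was selected to obtain early evidence and estimates of the effect size". Thirty subjects are expected to complete.

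**The concern.** The analysis sentence joins two things that do not fit. An ANOVA F test assumes equal means and looks for evidence against that. Failing to find such evidence is not evidence that the means are close, because it can equally reflect low precision. The result that section 3.8 hopes for is therefore one this test cannot deliver, and nothing in the plan tells the reader how to treat a non-significant result.

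The sentence also leaves out what section 12.2 says the study is for. An F test gives neither the size nor the direction of the difference between a microdosing paradigm and standard burst, and no estimate or interval is specified.

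Finally, the sentence compares follow-up visits. In this crossover each visit mixes all three paradigms across the groups, so a comparison of visits is not a comparison of paradigms.

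**Working it through.** The plan has no power, SD, alpha or margin to reproduce. The check has three parts.

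**1. What the test can conclude.** With paradigm means μ(standard), μ(5:5) and μ(5:10), the ANOVA null is that all three are equal. Rejection supports a difference, and non-rejection leaves the question open. An equivalence conclusion needs the reverse: a null that the difference is at least as large as a margin M, rejected when the confidence interval lies inside ±M. The plan has no M and no interval.

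**2. Visits against paradigms.** The three sequences in section 4.2 form this layout:

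| | Visit 1 | Visit 2 | Visit 3 |
|---|---|---|---|
| Group 1 | standard | 5:5 | 5:10 |
| Group 2 | 5:5 | 5:10 | standard |
| Group 3 | 5:10 | standard | 5:5 |

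With equal group sizes and no period effect, every visit mean has expectation [μ(standard) + μ(5:5) + μ(5:10)]/3. The paradigm effects cancel, so a literal comparison of visits tests period.

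**3. How often a real difference would be missed (illustration only).** From the documents: 30 completers (section 12.2), three paradigms per subject. Assumed: 0-100 mm VAS, two-sided alpha 0.05, no period or carry-over effect, equal SD for all pairwise within-subject differences (SDd), and a largest true paradigm difference of 10 mm.

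- Error df = (30 − 1) × (3 − 1) = 58. The critical value F(0.95; 2, 58) is 3.156.
- The variance of a within-subject difference is twice the error variance, so error variance = SDd²/2.
- Noncentrality λ = 30 × Σ(μᵢ − μ̄)² / (SDd²/2).
- Evenly spaced means (0, 5, 10): Σ = 25 + 0 + 25 = 50. At SDd 20, λ = 30 × 50/200 = 7.5.
- One mean apart, (0, 0, 10) or (0, 10, 10): Σ = 66.67. At SDd 20, λ = 30 × 66.67/200 = 10.0.
- P(non-significant) is the noncentral F probability below 3.156.
- 95% CI half-width for one difference = t(0.975; 58) × SDd/√30 = 2.0017 × SDd/5.477.

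| SDd (mm) | Non-significant, one mean apart | Non-significant, evenly spaced | 95% CI half-width (mm) |
|---|---|---|---|
| 10 | <0.1% | 0.1% | 3.7 |
| 15 | 3.5% | 10.0% | 5.5 |
| 20 | 20.6% | 33.7% | 7.3 |
| 25 | 41.0% | 53.4% | 9.1 |
| 30 | 56.5% | 66.3% | 11.0 |

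For a fixed 10 mm spread, even spacing gives the smallest Σ and so the highest miss rate. The two patterns therefore bound the result. Including period as a factor reduces the error df to 56 and changes no miss rate by more than 0.1 percentage points.

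**The case against.** The strongest reply is that the plan promises no equivalence conclusion. The objectives compare differences, section 3.8 is conditional risk-benefit prose, and the questioned phrase may simply be an awkward way of stating the null. The feasibility status and the absence of a power calculation are disclosed. A margin with two one-sided tests belongs to a confirmatory trial.

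Most of this stands. A reader might infer that the sponsor will declare equivalence from a non-significant p value; no section says so. A reader might also infer that the study is invalid because it lacks a margin or was not sized for equivalence. That does not follow for a study whose stated purpose is early evidence and estimation.

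On visits, the same sentence ends by naming the paradigms, and each subject's visit assesses exactly one paradigm. A comparison by paradigm is probably what is meant, and the documents do not support a claim that the analysis will be run by calendar visit.

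What remains is narrower. If equivalence only means the null, the sentence should say so, because section 3.8 uses the same idea for the benefit. The estimation aim does not answer the point either, since section 12.1 specifies no estimate.

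**Conclusion.** The point holds in limited form. The only analysis sentence names a hypothesis that its test cannot support, specifies no estimate or interval, and uses visits where paradigms are almost certainly meant. The plan neither states nor prevents a misreading of non-significance as equivalence.

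The size of that risk in this trial cannot be fixed from the documents. Under the stated assumptions it is negligible at an SD of 10 mm, small to moderate at 15 mm (3.5-10.0%) and substantial from 20 mm upward (20.6-33.7%, rising to 56.5-66.3% at 30 mm). Smaller true differences would be missed more often. The conclusion about the test itself needs none of these assumptions. Severity is minor to should-fix.

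**What to change.** Replace the last sentence of section 12.1 with text such as:

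*VAS, EQ-5D and satisfaction scores will be compared between the three stimulation paradigms by repeated-measures ANOVA, with period as a factor and no difference between paradigms as the null hypothesis. For VAS, each within-subject difference (microdosing minus standard) will be reported with its 95% confidence interval. A non-significant test will not be interpreted as equivalence.*

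This remains consistent with the primary endpoint in section 4.4.1: a common baseline cancels from the within-subject difference. In section 3.8, add that this feasibility study estimates the difference and is not designed to establish equivalency.

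A margin is optional, needed only if the sponsor wants a formal conclusion. It should then be justified and fixed before data are seen, with either two one-sided tests or a one-sided non-inferiority rule. The latter may suit, since section 3.0 allows that "it is possible that the new stimulation parameters will instead improve pain relief". The plan should also say how the two comparisons with standard are handled. For an assumed 10 mm margin and a true difference of zero, 30 completers give power of about 95, 71, 40 and 14% for two one-sided 5% tests at SD 15, 20, 25 and 30 mm. For one-sided 2.5% non-inferiority the figures are 94.8, 76.8, 57.7 and 43.5%.

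The core change costs a few sentences and no extra subjects, visits or data. The downside is that the sponsor gives up the equivalence wording.
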